## **5.4 Screen failures**

Screen failures are defined as study participants who consent to participate in the clinical study but are not subsequently randomly assigned to study treatment. A minimal set of screen failure information is required to ensure transparent reporting of screen failure study participants to meet the Consolidated Standards of Reporting Trials publishing requirements and to respond to queries from regulatory authorities. Minimal information includes demography, screen failure details, eligibility criteria, and any SAE.

Individuals who do not meet the criteria for participation in this study (screen failures) may be rescreened following discussion with the UCB Study Physician (Section 5.5).

Tests that result in ALT, AST, or ALP up to 25% above the exclusion limit may be repeated once for confirmation. This includes rescreening.

## 5.5 Rescreening

Study participants may be rescreened once under conditions such as the following:

- Study participant falls outside the Screening Period
- If a study participant does not meet the inclusion criteria at Screening or on Day -1 due to an out-of-range laboratory result or a minor illness, he/she can be rescreened once at the discretion of the Investigator. Provided all inclusion criteria are met at the second screening, the study participant can be included.

Study participants may be included if the repeat values for the laboratory screening criteria are within normal ranges and/or if repeat values show normalization of the out-of-range safety laboratory values, and/or after the study participant makes a complete recovery from the mild or moderate illness and if all other screening criteria are met.

Rescreened study participants are assigned a new study participant number from the number assigned at the initial screening.

## 6 IMP/INVESTIGATIONAL DEVICE PRESENTATION (FUNCTIONAL SECONDARY PACKAGING)

In this study, the term IMP refers to the bimekizumab drug product. The term device presentation refers to 4 different injection device presentations (bimekizumab-SS-1mL, bimekizumab-SS-2mL, bimekizumab-AI-1mL, and bimekizumab-AI-2mL) that are comprised of drug product (IMP) associated with a functional secondary packaging.

Bimekizumab will be supplied by UCB Clinical Trial Supply Operations or designee as a clear to opalescent, colorless to slightly yellow-brown, sterile, preservative-free solution, suitable for injection by sc administration, in either a 1mL PFS or a 2mL PFS at a nominal concentration of 160mg/mL (55mM sodium acetate, 220mM glycine, 0.04% polysorbate 80 at pH 5.0) for sc administration.

### 6.1 Treatments to be administered

The treatments to be administered are presented in [Table 6-1](#).

**Table 6-1: Treatments to be administered**

Study Treatment	Bimekizumab-SS-2mL	Bimekizumab-SS-1mL	Bimekizumab-AI-2mL	Bimekizumab-AI-1mL
Drug product:	2mL PFS	1mL PFS	2mL PFS	1mL PFS
All treatments: a nominal concentration of 160mg/mL in 55mM sodium acetate, 220mM glycine and 0.04% (w/v) polysorbate 80 at pH5.0				
Total dose:	320mg	320mg	320mg	320mg
Duration of treatment:	Single dose	Single dose	Single dose	Single dose

**Table 6-1: Treatments to be administered**

Study Treatment	Bimekizumab-SS-2mL	Bimekizumab-SS-1mL	Bimekizumab-AI-2mL	Bimekizumab-AI-1mL
Number of injections:	1x320mg	2x160mg	1x320mg	2x160mg
Route of administration	sc	sc	sc	sc
Site of injection:	Thigh (left or right)	Thigh (1 in left and 1 in right)	Thigh (left or right)	Thigh (1 in left and 1 in right)
Device presentation	2mL SS	1mL SS	2mL AI	1mL AI

AI=auto-injector; PFS=prefilled syringe; sc=subcutaneous; SS=safety syringe

The IMP will be given in the thigh without massage. For bimekizumab-SS-1mL, the injection should last approximately 10-15 seconds. For bimekizumab-AI-1mL, the injection should continue until a second click is heard (to give an injection time of up to 15 seconds). For the administration of the 2x1mL, each sc injection should be given in a separate thigh (but at the same relative site of the thigh) with a maximum time of 60 seconds between injections. The exact timing of the injection(s) should be recorded in the electronic Case Report Form (eCRF). For bimekizumab-SS-2mL, the injection should last approximately 15-20 seconds. For bimekizumab-AI-2mL, the full dose will be injected in approximately 20 seconds.

Further details on how to proceed in the event of malfunction of any of the devices will be provided in the IMP handling manual.

### 6.1.1 Medical device presentations

The device presentations provided for use in this study are the Nemera Safe'n'Sound SS device and the Ypsomed Ypsomate AI device.

Instructions for medical device presentation use are provided in the respective Instructions for Use (IFU).

All medical device presentation deficiencies, including malfunction use error, and inadequate labelling, shall be documented and reported by the Investigator throughout the study (see Section 8.3.7) and appropriately managed by the Sponsor.

#### 6.1.1.1 Bimekizumab-SS

The bimekizumab-SS is single-use PFS with a passive-needle safety mechanism. The bimekizumab-SS-1mL consists of a 1mL glass PFS and the bimekizumab-SS-2mL consists of a 2mL glass PFS, both containing bimekizumab drug product within customized Nemera Safe'n'Sound device presentations.

**Figure 6-1: Bimekizumab-SS-1mL**

SS=safety syringe

**Figure 6-2: Bimekizumab-SS-2mL**

SS=safety syringe

#### 6.1.1.2 Bimekizumab-AI

The bimekizumab-AI is single-use AI with a passive-needle safety feature. The bimekizumab-AI-1mL consists of a 1mL glass PFS and the bimekizumab-AI-2mL consists of a

2mL glass PFS, both containing bimekizumab drug product within a customized Ypsomed Ypsomate device presentation.

**Figure 6-3: Bimekizumab-AI-1mL**

AI=auto-injector

**Figure 6-4: Bimekizumab-AI-2mL**

AI=auto-injector

## **6.2 Preparation, handling, storage, and accountability requirements**

The Investigator or designee must confirm appropriate temperature conditions have been maintained during transit for all study treatment received and any discrepancies are reported and resolved before use of the study treatment.

Only study participants enrolled in the study may receive study treatment and only authorized site staff may supply or administer study treatment. All study treatments must be stored in a secure, environmentally controlled, and monitored (manual or automated) area in accordance

with the labeled storage conditions with access limited to the Investigator and authorized site staff.

The Investigator, institution, or the head of the medical institution (where applicable) is responsible for study treatment accountability, reconciliation, and record maintenance (ie, receipt, reconciliation, and final disposition records).

In case an out-of-range temperature is noted, it must be immediately reported as per instructions contained in the IMP Handling Manual.

Appropriate accountability forms that reflect the receipt and use of the IMP and the investigational device presentations including IMP will be supplied to the investigational site. Details of any loss of the IMP and/or injection investigational device presentations due to breakage or wastage, non-use, destruction at the study site, or return to the Sponsor or designee must also be recorded on these forms. All supplies and pharmacy documentation must be made available throughout the study for UCB (or designee) to review.

The Investigator (or designee) is responsible for retaining all used, unused, and partially used IMP and investigational device presentations until returned or destroyed. The Investigator may assign some of the Investigator's duties for drug accountability at the study site to an appropriate pharmacist/designee.

The device presentations should be stored with a proper study participant identification number until the study has been completed. UCB will then instruct the Investigator to destroy them. Used device presentations can be stored at room temperature, preferably placed in the original packaging. Further details are provided in the IMP Handling Manual.

The IMP and investigational device presentations intended for the study cannot be used for any other purpose than that described in this protocol.

### **6.2.1 Retention samples**

The retention samples needed on site will represent 5 times the quantity needed to perform all release tests required; 500 samples will be retained. Sufficient quantities of each formulation will be provided to the sites for retention and study conduct purposes.

Retention samples will be chosen at random by the Investigator and will be kept on site as retention samples to comply with Food and Drug Administration requirements Code of Federal Regulations (CFR)320, parts 38 and 63.

### **6.3 Measures to minimize bias: randomization and blinding**

This is an open-label study.

A PAREXEL Biostatistician will write the randomization program and will provide a dummy output of the randomization for review in order to ensure compliance to study requirements.

Study participant treatment assignment will be random throughout the study. Study participants will be randomized in a 1:1:1:1 ratio to each treatment group as described in Section 4.1.

Copies of the randomization list will be sent before the start of the study to the following recipients:

- ClinBase™ setup designer

---

- Sponsor Drug Safety staff for SAE reporting
- Bioanalytical staff
- Site pharmacist and Pharmaceutical Services staff (for dispensing IMP)

Pharmacokinetic concentration data will not be available to the study team until after the last scheduled procedure for the last study participant in the study, so the decision to replace participants who dropped out or are missing PK visits due to COVID-19 can be made in an unbiased manner.

At the Screening Visit, each study participant will be assigned a unique 5-digit number from a range of numbers supplied by UCB. Once the Investigator determines that the study participant is eligible for the study, the study participant will be manually assigned to the next available randomization number by the Investigator or designee on the evening of Day -1. Each specific randomization number is tied to the treatment allocation on the randomization schedule, which can then be dispensed by the site pharmacist. This randomization number will also be recorded in the eCRF (ie, ClinBase; see Section 10.1.6).

The study design accounts for a 10% rate of dropouts and/or non-evaluable participants (participants with missing PK visits that are expected to impact derivation of  $C_{max}$  and/or AUC). The dropout rate will be closely monitored and if this 10% rate is likely to be exceeded, due to unforeseen circumstances during the COVID-19 pandemic, then participants may be replaced. The number of replacements will be discussed and agreed with the Sponsor. Replacement participants will be assigned the next available randomization number.

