e Vital signs include BP, pulse rate, and tympanic body temperature. Body temperature only will be measured at outpatient visits without regular vital signs measurement (Days 4, 5, 6, 7, 8, 10, 13, 16, 19, 22, and 28).

f During the inhouse treatment period, vital signs and ECGs should be measured/taken prior to blood sampling, where applicable, with the study participant resting in the supine position for at least 3 minutes. Vital signs and ECGs will be measured on Day 1 at predose, at 1.5h, 5h, and 11h postdose, on Day 2 at 24h postdose, and on Day 3 at 48 hours postdose, then on Days 9, 25, 56, 84, 112, and 140.

g Height will be recorded only at the Screening Visit.

h As this is a single-dose study, device presentation deficiencies are only to be captured on Day 1 (ie, the day when IMP is administered during the inhouse treatment period).

i Serology variables include HbsAg, HBc-Ab, HCV-Ab (both IgG and IgM), HIV1-Ab, HIV1-Ag, and HIV-2 Ab.

j Blood sampling for hematology (including coagulation and hemostasis) and clinical chemistry will be performed at the Screening Visit, and Days -1, 2, 9, 25, 56, 84, 112, and the SFU Visit.

k Urinalysis via dipstick will be performed at Screening, Day-1, Days 2, 9, 25, 56, 84, 112, and 140.

l The PK sampling time points will be as follows: predose within 15 minutes at maximum before dosing, and 1.5h, 5h, 24h, 48h postdose, and from Day 4 onwards at every visit (ie, Days 4 to 10, 13, 16, 19, 22, 25, 28, 56, 84, 112, and 140).

m ADAb samples will be taken predose and on Days 13, 28, 56, 84, 112, and 140; blood samples will be processed as specified in the laboratory manual.

n Pregnancy tests will be performed at the Screening Visit, Day-1, Days 28, 56, 84, 112, and Day 140. Prior to dosing, the test should be performed in serum; post dosing the test may be performed in urine. The FSH test will be performed in postmenopausal women at the Screening Visit.

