### **10.1.4 Data protection**

UCB staff (or designee) will affirm and uphold the study participant's confidentiality. Throughout this study, all data forwarded to UCB (or designee) will be identified by the study participant's randomization number.

The Investigator agrees that representatives of UCB, its designee, representatives of the relevant IEC, or representatives of regulatory authorities will be allowed to review that portion of the study participant's primary medical records that directly concerns this study (including, but not limited to, laboratory test result reports, ECG reports, admission/discharge summaries for hospital admissions occurring during a participant's study participation, and autopsy reports for deaths occurring during the study).

The study participant must be informed that his/her personal study-related data will be used by the Sponsor in accordance with local data protection law. The level of disclosure must also be explained to the study participant.

The study participant must be informed that his/her medical records may be examined by Clinical Quality Assurance auditors or other authorized personnel appointed by the Sponsor, by appropriate IEC members, and by inspectors from regulatory authorities.

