## 2.2 Study variables

### 2.2.1 Pharmacokinetic variables

The PK parameters provided in this section will be derived from the plasma concentration data.

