#### 2.2.1.1 Primary pharmacokinetic variables

The primary PK parameters are:

- AUC: Area under the plasma concentration-time curve from time zero to infinity, calculated as calculated as  $AUC = AUC_{0-t} + C_{last}/\lambda_z$ , where  $C_{last}$  is the last observed quantifiable plasma drug concentration and  $\lambda_z$  is the apparent terminal elimination rate constant
- $AUC_{(0-t)}$ : Area under the plasma concentration-time curve from time zero to the last quantifiable concentration, as determined using the linear trapezoidal rule
- $C_{max}$ : Maximum observed plasma drug concentration

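### Protocol 6.3 gives the randomization list to the bioanalytical laboratory before the study starts, with no stated need and no masking, although every primary endpoint comes from its concentrations

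*Protocol*

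**What the plan says.** Protocol 6.3 describes the study as open-label, then states: "Copies of the randomization list will be sent before the start of the study to the following recipients". Four entries follow: the ClinBase setup designer, sponsor drug safety staff, "Bioanalytical staff", and the site pharmacist with pharmaceutical services staff. The safety entry (SAE reporting) and the pharmacy entry (dispensing) carry a purpose. The bioanalytical entry does not.

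The list reveals the arm directly: "Each specific randomization number is tied to the treatment allocation on the randomization schedule". Protocol 10.1.4 adds that "all data forwarded to UCB (or designee) will be identified by the study participant's randomization number".

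On the endpoints, SAP 2.2.1 says: "The PK parameters provided in this section will be derived from the plasma concentration data". The primary parameters are AUC, AUC(0-t) and Cmax, the last defined in SAP 2.2.1.1 as "Maximum observed plasma drug concentration". Protocol 9.4.1 and SAP 9.2.1 require the 90% confidence intervals for all three to lie within 0.8 to 1.25.

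Protocol 6.3 contains one related safeguard, repeated in SAP 4.2.1. It withholds concentrations from the study team until the last participant's last procedure, so that decisions to replace participants are unbiased.

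**The concern.** In an open-label trial the participant and the injecting staff cannot avoid knowing the device. The laboratory can avoid it, because a plasma sample can be analysed without reference to the arm. The plan nevertheless releases the allocation to the people who generate the primary data, before any sample exists.

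The existing safeguard runs in one direction only. It keeps concentrations from the study team, but it does not keep the allocation from those producing the concentrations. Any room for influence would lie in laboratory decisions such as repeat analysis, run acceptance and sample rejection. Neither document gives rules for these. A difference between arms introduced there would pass into all three primary parameters and into both device comparisons.

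**Working it through.** **1. Is there a visible reason for the laboratory to know the arm?**

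- Product: Protocol Table 6-1 gives "All treatments: a nominal concentration of 160mg/mL in 55mM sodium acetate, 220mM glycine and 0.04% (w/v) polysorbate 80 at pH5.0", with a total dose of 320 mg in every arm. No dose difference could guide dilution.
- Control: Protocol 4.1 lists four active arms and no placebo, so there are no placebo samples to leave out.
- Schedule: Table 1-1, footnote l, sets one timetable for all arms, beginning "The PK sampling time points will be as follows: predose within 15 minutes at maximum before dosing".
- Assay text: the pharmacokinetic and immunogenicity sections (Protocol 8.6 and 8.10; SAP 4.2.1, 9.1.1 and 10.1) state no need for the allocation and no masking of analysts.

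No reason is visible in either document.

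**2. Scale of what is exposed.** Planned PK samples per participant, from the same footnote:

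| Time points | Samples |
|---|---|
| Predose | 1 |
| 1.5, 5, 24, 48 h | 4 |
| Days 4 to 10 | 7 |
| Days 13, 16, 19, 22, 25, 28 | 6 |
| Days 56, 84, 112, 140 | 4 |
| **Total** | **22 (21 postdose)** |

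With 100 participants per arm (Protocol 9.9), before dropouts:

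- per arm: 22 × 100 = 2,200
- per comparison (two arms): 22 × 200 = 4,400
- whole study: 22 × 400 = 8,800, of which 21 × 400 = 8,400 are postdose.

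These counts describe workload, not bias.

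**3. Would a small differential error matter? (Illustration only.)** The plan's own figure comes first. With CV 33%, the log-scale SD is σ = √ln(1 + 0.33²) = 0.3215. With n = 93 per group the standard error of the log ratio is 0.3215 × √(2/93) = 0.0471. Two one-sided t-tests at 5% each, with 184 degrees of freedom and a true ratio of 0.9, give 80.07% power; n = 92 gives 79.69%. The stated 93 per group is reproduced.

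Now take a true ratio at the limit, 0.80, and suppose that reported test-arm concentrations are raised by a fraction s, so that the apparent ratio is 0.80 × (1 + s). The values of s are assumptions; the documents give none. The chance of falsely passing on one parameter, with 93 per group, is:

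| s | CV 33% | CV 25% |
|---|---|---|
| 0 | 5.0% | 5.0% |
| 1% | 7.6% | 8.5% |
| 2% | 11.0% | 13.6% |
| 3% | 15.4% | 20.4% |
| 5% | 27.0% | 38.3% |

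All three parameters must pass, so these are not overall error rates. They show only that small one-directional errors matter near the limit, not that such errors are likely.

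**The case against.** The strongest reply is that nothing here is contradictory. The study is declared open-label, no masked assay is promised, and a concentration is a measurement rather than a judgement. Moving a geometric mean ratio over about 100 participants per arm would take systematic errors in one direction, and no mechanism is shown. Exclusion of participants and off-window samples is decided at the Data Evaluation Meeting, not in the laboratory.

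The link from list to sample is also inferred. Protocol 10.1.4 concerns data forwarded to the sponsor or its designee, not tube labels, and participants also hold a separate 5-digit number from Screening. Laboratory instructions that were not supplied may cover labelling, repeats and masking, or may set out a real need for the list.

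Much of this stands as a limit. Whether analysts could match a sample to an arm in practice is unknown, and a need described elsewhere cannot be ruled out. A missing purpose is not decisive alone, since the ClinBase setup designer has none either. Nor is the assay the only step that could be masked: choosing terminal-phase points for the elimination rate (SAP 2.2.1.2) is another.

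The objections do not supply a reason for the release. The open-label label explains why the site knows the device, not why analysts should. The Data Evaluation Meeting does not govern repeat analysis or run and sample rejection inside the laboratory. If masking is specified elsewhere, Protocol 6.3 still authorises an unrestricted release and needs to be reconciled with it.

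**Conclusion.** The concern holds as an avoidable exposure, not as evidence of bias. The protocol sends the allocation, before the study starts, to staff whose results determine all three primary parameters in both comparisons, and neither document gives an assay need or masking.

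The size of any bias cannot be derived from the documents. Confidence is moderate, because sample labelling and laboratory procedures are not described in either document. The change is worth making because it protects every primary conclusion at very little cost, but the point does not by itself undermine the design.

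**What to change.** In Protocol 6.3, delete the bioanalytical entry from the list of recipients. Add one sentence stating that sample analysis, including any repeat analysis or rejection of samples, is carried out without access to treatment allocation until concentrations are final.

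If the laboratory needs the list, state why and limit it to named functions that do not analyse samples.

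If the list has already been sent, which is possible because Protocol 2.3.1 speaks of enrolment restarting, restrict access for staff analysing samples. In that case keep an accurate record of what was released and when, rather than simply deleting the entry.

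The cost is administrative: one entry removed, one sentence added and one instruction to the laboratory. Under Protocol 10.1.1 the change needs ethics committee approval, and it could travel with another amendment. No participants, samples or procedures are added.

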#### **6.4 Treatment compliance**

All IMP will be administered by the Investigator or his/her appropriately trained designee.

#### **6.5 Concomitant medication(s)/treatment(s)**

##### **6.5.1 Permitted concomitant treatments (medications and therapies)**

The following concomitant medications are permitted during the study:

- Acetaminophen/paracetamol (maximum 2g/day)
- Oral contraceptives
- Hormonal postmenopausal treatment
- Herbal remedy or food supplements (eg, vitamins) within the recommended daily dose limits
- Short-term intake of over-the-counter/non-prescription drugs is allowed if judged by the Investigator to have no potential for drug-drug interactions with the IMP

##### **6.5.2 Prohibited concomitant treatments (medications and therapies)**

With the exception of those medications listed in Section 6.5.1 and medications necessary for the treatment of TEAEs per Investigator discretion, no prescription or nonprescription medicines are allowed within 30 days (or 5 half-lives of the respective medication, whichever is longer) prior to randomization and until the SFU Visit (Day 140).

